4.1.1 Treatment Design

This will be a two-arm, multi-center, prospective randomized trial of two types of lifestyle modification in obese women with unexplained infertility who will be randomized to either an intensive lifestyle modification with weight loss and increased physical activity or a standard lifestyle modification consisting of increased physical activity for 16 weeks prior to initiating infertility treatment with an oral drug, clomiphene, to stimulate follicular development followed by intrauterine insemination (IUI). The lifestyle modifications will be open label with adequate allocation concealment and the randomization ratio will be equal between modifications (1:1).

The appropriate study candidates will be recruited from the main sites of the Reproductive Medicine Network and their ancillary partners. Recruited subjects will meet the inclusion and exclusion criteria detailed below. Monitoring of this trial at all sites will be conducted by the RMN Data Coordination Center, with progress reports provided to the RMN Data and Safety Monitoring Board (DSMB) no less than every three months in order to review trial progress and subject safety.

4.1.2 Study Population

Three hundred eighty (380) infertile obese ovulatory women actively seeking pregnancy (190 per treatment arm), age 18-40 years, will be enrolled in the participating sites. The overall goal of the inclusion/exclusion criteria is to identify a population of healthy infertile women who are regularly ovulating. These will include a normal uterine cavity with at least one patent tube and a partner with a motile sperm count of at least 5 million in the ejaculate. If existing medical records are used to verify inclusion or exclusion criteria, the site should keep a copy of these in the source documents. A general list of exclusionary medications requiring a washout period is found in the appendix. The list is not exhaustive and questionable medications can be looked up to see if they belong to one of the families of exclusionary medications, or the Project Leader ([name]) and/or DCC can be queried.

5 Selection and Enrollment of Subjects

5.1 Inclusion Criteria

1. Women ≥ 18 to ≤ 40 years of age, with one or more years infertility history, desirous of conceiving, regularly ovulating (defined as 9 or more menses per year), at initiation of participation.
2. BMI ≥ 30 kg/m² obtained at screening visit.
3. Normal uterine cavity and at least one open fallopian tube confirmed by hysterosalpingography (HSG), sonohysterography (SHG), or laparoscopy/hysteroscopy in the last three years preceding enrollment into the study. An uncomplicated intrauterine non-IVF pregnancy and uncomplicated delivery and postpartum course resulting in live birth within the last three years will also serve as sufficient evidence of a patent tube and normal uterine cavity as long as the subject did not have, during the pregnancy or subsequently, risk factors for Asherman's syndrome or tubal disease or other disorder leading to an increased suspicion for intrauterine abnormality or tubal occlusion.
4. Evidence of ovarian function/reserve as assessed by day 3 (+/-2 days) FSH ≤ 10 IU/L with Estradiol ≤ 70 pg/mL OR serum AMH ≥ 1 ng/mL within one year prior to study initiation.
5. Normal or corrected thyroid function within one year of study initiation.
6. Normal or corrected prolactin level within one year of study initiation.
7. In general good health, not taking any medications which could interfere with the study (e.g., FSH, insulin sensitizers - see Appendix for full list).
8. Ability to have inseminations following hCG administration
9. Male partner with total motile sperm in the ejaculate of at least 5 million sperm, within one year of study initiation
10. Able to have intercourse and collect semen for insemination

5.2 Exclusion Criteria

1. Currently pregnant or successful pregnancies within 12 months of initiating participation. Clinical intrauterine miscarriages prior to initiating participation, within ASRM guidelines: subjects 35 and over must wait six months, while subjects under 35 must wait 12 months. No exclusion for biochemical pregnancies.
2. Undiagnosed abnormal uterine bleeding.
3. Suspicious ovarian mass.
4. Subjects on oral contraceptives, depo-progestins, or hormonal implants (including Implanon). A two month washout period will be required prior to screening for patients on these agents. Longer washouts may be necessary for certain depot contraceptive forms or implants, especially when the implants are still in place. A one-month washout will be required for patients who have taken oral cyclic progestins.
5. Known 21-hydroxylase deficiency or other enzyme defect causing congenital adrenal hyperplasia.
6. Type I or Type II diabetes mellitus, or if receiving antidiabetic medications.
7. Known significant anemia (Hemoglobin <10 g/dL).
8. History of deep venous thrombosis, pulmonary embolus, or cerebrovascular event.
9. Known heart disease (New York Heart Association Class II or higher).

10. Known liver disease (defined as AST or ALT >2 times normal, or total bilirubin >2.5 mg/dL).
11. Known renal disease (defined as BUN >30 mg/dL or serum creatinine > 1.4 mg/dL).
12. History of, or suspected cervical carcinoma, endometrial carcinoma or breast carcinoma.
13. History of alcohol abuse (defined as >15 drinks/week) or binge drinking of ≥ 6 drinks at one time).
14. Known Cushing's disease.
15. Known or suspected adrenal or ovarian androgen secreting tumors.
16. Allergy, known hypersensitivity or contraindication to the treatment medications used in this study including orlistat (This will include patients with chronic malabsorption syndrome or cholestasis or clomiphene (previous change in vision).
17. Couples with previous sterilization procedures (e.g. vasectomy, tubal ligation) whether or not it has been reversed.
18. Subjects with untreated poorly controlled hypertension defined as a systolic blood pressure ≥ 160 mm Hg or a diastolic ≥ 100 mm Hg obtained on two measures obtained at least 60 minutes apart.
19. Subjects who have undergone a bariatric surgery procedure in the past or are in a period of acute weight loss (defined as a weight loss of greater than 5% body weight in the last 6 months).
20. Known severe endometriosis
21. Anovulation or oligo-ovulation including hypothalamic amenorrhea, polycystic ovary syndrome, etc.
22. Donated semen.
23. Couples in which either partner is legally married to someone else.
24. Medical conditions that are contraindications to pregnancy.
25. Presence of severe, untreated psychiatric illness (major depression, substance abuse, eating disorder, etc.) that would, in the opinion of the site investigator, interfere with the patient's ability to successfully complete the study.
26. Any additional medical conditions that would be a contraindication to orlistat.
27. Any contraindication to study requirements including diet recommendations and activity requirements.
28. Currently participating in a lifestyle intervention program (such as Weight Watchers, Atkins Diet, Curves)
29. History of Gout.
30. History of pelvic radiation

5.3 Study Termination Criteria

1. Development or suspicion of an allergic or serious adverse reaction to any of the medications in the study.
2. Uncontrolled hypertension.
3. Persistent ovarian cyst > 30 mm mean diameter that does not resolve in two cycles.
4. Serious or severe Ovarian Hyperstimulation Syndrome (OHSS).

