4.1 Overview

The flowchart (Figure 3) summarizes this study which will consist of infertility treatment commencing with randomization at equal allocation (1:1) to two interventions (Phase I), an intensive lifestyle modification which includes caloric restriction primarily with meal replacements (Nutrisystem), use of a weight loss medication (Alli), and physical activity recommendations, and a less intensive lifestyle modification intervention focused on increasing physical activity with weight maintenance. This will serve as the comparison group. After completion of the 16 week lifestyle intervention, subjects will receive 3 cycles of ovarian stimulation with an oral medication (clomiphene citrate), triggered ovulation with hCG, and a single intrauterine insemination per cycle (Phase II). During the infertility treatment phase, subjects will be encouraged to maintain their weight and activity levels achieved during the initial intervention. Subjects who conceive will be followed to the point of documented viable intrauterine pregnancy, and then will be seen once per trimester for a brief visit with serum and urine collection. All pregnancies will be followed until completion (Phase III). Subjects who deliver viable infants will be offered participation in our Pregnancy Registry (Phase IV). The details of the Pregnancy Registry protocol can be found in that protocol document.

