6.1.1 Determine Baseline Physical Activity

Subjects will be dispensed a Fitbit Physical Activity monitor during the randomization visit which will be used to determine average daily steps over a week's time.

Standard Physical Activity Intervention: This will be identical to the physical activity described above for the intensive physical activity group. There will be no dietary recommendations, no use of meal replacements, and no use of anti-obesity drugs. Subjects will have the same monitoring schedule both on site and off site as subjects in the intensive lifestyle modification.

Conception during Lifestyle Modification We will encourage intercourse without barriers during the lifestyle modification phase and welcome any pregnancies which happen. They will be managed identically as though that occur during the empiric infertility treatment phase of this study (Phase II below). Of course such pregnancies will be analyzed by treatment group according to intention-to-treat (ITT) principles. We are using safe and widely utilized lifestyle modifications. We are using an OTC weight loss drug, Alli, that has no known early adverse pregnancy effects and we will immediately discontinue it if pregnancy occurs. The ability to conceive at all points in this study will increase the appeal to participate and also the external validity of our results. No one with infertility wants to stop attempting pregnancy as part of infertility treatment. This also led us to reject using the oral contraceptive pill as a control arm for unexplained infertility.

Phase II – Standardized infertility treatment

After completion of Phase I (or 16 weeks of pretreatment), all subjects will enter Phase II. This phase will be universally administered to all participants in an open label, but standardized fashion. In this part of the study, subjects will receive three cycles of ovarian stimulation/hCG

trigger for ovulation/ timed IUI and followed by midluteal visit. We will clamp weight and activity in both groups and continue to monitor with the Fitbit and the Aria scale. We will modify and streamline the study procedures from our AMIGOS study.

Phase III – Pregnancy

There will be no treatment intervention during pregnancy, though we will continue to monitor weight and have trimester study visits.

Phase IV – Pregnancy Registry

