9.1 Phase I

There are no predetermined criteria for discontinuation during Phase I. Subjects will be allowed to continue in the trial even if they do not achieve the goals of the two interventions and eventually receive the infertility treatment in Phase II. However each subject will have to complete the 16 week pretreatment period before receiving the Phase II treatments. Subjects can not be accelerated into Phase II.

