9.1.1 Intensive Lifestyle Modification

Orlistat intolerance: Subjects who are unable to tolerate the dose of orlistat will be allowed to skip doses at specific mealtimes to ease symptoms or to discontinue altogether with continued intolerance based on the decision of the site PI.

Algorithm for poor responders: Subjects who fail to lose appropriate weight in the intensive lifestyle modification group or fail to meet physical activity goals in either group will be contacted by the study coordinator on a weekly basis to review reasons. We will pilot smart phone automated responses also within this trial. Drs. [name] and [name] will lead the training (prior to the start of the study) and supervision (through monthly conference calls) of the interventions as well as review on a weekly basis of persistent poor responders and excessive responders (see below).

Algorithm for excessive responders: Excessive and rapid weight loss can be associated with health risks including formation of gall stones, development of hypotension, loss of energy, but rarely by an attack of gout. Subjects will be counseled at the onset about these health risks and to avoid excessive weight loss. Excessive response will be defined as a weight loss exceeding an average of 2.5 pounds per week or 10 pounds in a 4 week period. Subjects who exceed this at a monthly visit will be counseled to increase their caloric intake, by approximately 300-500 kcal/d, to slow the weight loss to our prescribed limits. We will follow subjects with their weekly weights collected by their Fitbit Aria wireless scales, and discuss them at both monthly investigator conferences and weekly coordinator conferences until they meet our guidelines. We will monitor the Fitbit steps during the first month of the study online to ensure that subjects do not exceed our guidelines of increasing 500 steps a day. We will also review monthly Fitbit records to ensure that subjects do not exceed the 10,000 steps on a regular basis. Subjects who consistently exceed our guidelines (more than 7 days in a 28 day period) will be advised to lower their activity to meet guidelines, and this will become a topic for weekly study coordinator and monthly investigator phone conferences

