11.3.6 Establishment of Pregnancy Registry

We intend to establish a pregnancy registry for this trial to establish outcomes of pregnancy. Couples who conceive will be offered participation in the Pregnancy Registry and a separate informed consent form will be obtained if they choose to participate. We will track the outcomes of all randomized subjects who have a positive serum pregnancy screen during the course of this study. We will record biochemical pregnancies (defined as positive serum pregnancy screens without ultrasonically detected pregnancies), ectopic pregnancies, and all intrauterine pregnancy losses both before and after 20 weeks including missed abortions, spontaneous abortions, elective abortions, fetal demises, and stillbirths. We will review pregnancy and birth records of the mother and of the fetus to establish neonatal morbidity and mortality and the presence of fetal anomalies. This will be done for all subjects who conceive.

If they participate in the Pregnancy Registry, we will extract from these records concomitant medical and obstetrical conditions, exposure information on all other medical products used, including prescription products, over-the-counter (OTC) products, dietary supplements, vaccines, and insertable or implantable medical devices. We will file individual case reports for all congenital anomalies which will be considered a serious adverse event. Additionally we will provide to the FDA a written annual status report of the pregnancy registry as specified in the guidelines above. We intend at a minimum to perform an annual parent directed screening questionnaire to assess the infant's developmental milestones for the first three years after birth as recommended by the FDA and to review the child's CDC growth curve and medical records. The registry will follow children until age 3. A survey will be administered to the mother annually that will screen for cognitive, and neurodevelopment up to age 3. If medical issues arise from the survey, a medical record review will be performed for more extensive assessment.

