11.4 Adverse Event Reporting

11.4.1 Serious Adverse Events

All serious adverse events (SAEs) that occur from randomization at Phase I through thirty days after the last dose of study medication (orlistat, clomiphene, or hCG) must be reported or if the patient is pregnant, 6 weeks following delivery. A serious adverse event is defined as: fatal or immediately life-threatening; severely or permanently disabling; requiring or prolonging inpatient hospitalization; overdose (intentional or accidental); congenital anomaly; pregnancy loss after 20 weeks gestation; neonatal death up to 6 weeks after delivery; or, any event adversely affecting the study's risk/benefit ratio. Additionally, any event that, based on appropriate medical judgment, may jeopardize the subject's health and may require medical or surgical intervention to prevent one of the outcomes listed above is considered an SAE.

If an SAE occurs and is thought to be related to the study medication, the study medication will be discontinued.

The site PI will report the SAE by completing and signing the Serious Adverse Event Report Form [available in the "Study Forms" section of the RMN members-only website], and then emailing the document in PDF format to [contact]. Subjects will be identified by study number only. No other identifying information will be included on the form. The site PI must

determine and record on the SAE form whether the SAE is unanticipated or anticipated, and if it is related, possibly related, or unrelated to participation in the research.

DCC staff will enter the SAE information in the central database. The Safety Surveillance team, consisting of the DCC, NICHD research scientist and lead PI of the protocol, will analyze the SAE to determine if it meets the criteria listed in the OHRP 45CFR46 and/or FDA 21CFR312.32 & 3.14.80.

These determinations will dictate timeframes for sites' submission to the DCC, and the DCC's submission to the DSMB (**Table 12**):

[figure not shown]
Table 12: Types of Serious Adverse Events and their reporting requirements

TYPE	SITE	DCC
Unanticipated and related/possibly related SAE, fatal or life-threatening	Report to DCC within 1 business day of discovery	Notify DSMB by end of next business day of receiving site report
Other unanticipated and related/possibly related SAE	Report to DCC within 1 business day of discovery	Notify DSMB 5 business days of receiving site report

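### Section 5.3 item 1 ends study participation for a suspected allergic or serious drug reaction where other sections stop only the drug; in Phase I this falls mainly on the intensive arm, with a probably very small effect

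*Combined protocol and SAP*

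**What the plan says.** **The termination rule.** Section 5.3 (Study Termination Criteria), item 1, reads: "Development or suspicion of an allergic or serious adverse reaction to any of the medications in the study". Suspicion alone is enough, and every study medication is covered.

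**What other sections do with drug problems and with progress to Phase II.**
- Section 1.5 and the Phase II text in Section 6.1 state that all randomized women go on to the infertility treatment after 16 weeks, whatever their adherence or success.
- Section 9.1: "There are no predetermined criteria for discontinuation during Phase I".
- Section 9.1.1, on women who cannot tolerate orlistat, allows them to skip doses or "to discontinue altogether with continued intolerance based on the decision of the site PI". It states no exit from the trial.
- Section 11.4.1: "If an SAE occurs and is thought to be related to the study medication, the study medication will be discontinued".
- Section 7.2 (medication adjustment in Phase II) allows the drug to be withheld for the remaining cycles after an adverse reaction.

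**Which drugs are involved.** Section 11.4.1 sets the reporting window by the "last dose of study medication (orlistat, clomiphene, or hCG"). Of these three, only orlistat belongs to Phase I. For the standard arm in Phase I, Section 6.1.1 says: "There will be no dietary recommendations, no use of meal replacements, and no use of anti-obesity drugs". Both arms also receive prenatal vitamins (Section 7.2, randomization visit).

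**Follow-up and analysis.** Section 11.3.6: "We will track the outcomes of all randomized subjects who have a positive serum pregnancy screen during the course of this study". Section 4.1: "All pregnancies will be followed until completion (Phase III"). The end-of-Phase-2 visit in Section 7.2 is also the visit for study withdrawal. Section 10.9 analyses all randomized women by assigned arm and leaves imputation to be used if needed.

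**The concern.** Suppose a woman in the intensive arm has a suspected serious reaction to orlistat in week 6. One site could end her participation under 5.3. Another could stop orlistat under 11.4.1, keep her on the remaining Phase I programme and take her on to clomiphene/IUI under 6.1 and 9.1. Nothing in the documents supplied says which section governs.

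The first reading gives the worse result. She loses up to three treatment cycles because of a drug that is not used in those cycles. The loss falls mainly on one arm, because a woman in the standard arm has no orlistat to react to. The intent-to-treat analysis still counts her in the intensive arm.

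A second, narrower matter is follow-up. A pregnancy found while she is in the study is tracked to its end. If she leaves not pregnant, the documents supplied schedule no contact after the withdrawal visit to learn whether she conceived and delivered within the period over which the other women are observed.

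**Working it through.** **1. The sections side by side, for a suspected serious orlistat reaction in Phase I**

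| Section | Consequence | Relation to 5.3 item 1 |
|---|---|---|
| 5.3 item 1 | Study termination | – |
| 1.5, 6.1 | All randomized women proceed to Phase II | In tension |
| 9.1 | No predetermined Phase I discontinuation criteria | In tension |
| 11.4.1 | Drug stopped if the event is thought related | Compatible, but goes less far |
| 7.2 (Phase II drugs) | Drug may be withheld | Different phase; goes less far |
| 9.1.1 | Doses skipped or orlistat stopped | Different event (intolerance); shows the drug-stopping approach only |

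**2. The plan's own sample size**

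Inputs from Section 10.4.1: good birth outcome 0.25 versus 0.40, two-sided 0.05, 80% power, 20% dropout. With a pooled two-proportion test and no continuity correction, n = 152 per arm, and 152 / (1 − 0.20) = 190. Both match Table 11.

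Power = Φ{ [d√n − 1.96 √(2p̄(1 − p̄))] / √(p₁(1 − p₁) + p₂(1 − p₂)) }, where d = p₂ − p₁ and p̄ is the mean of the two proportions.

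- n = 152: (0.15 × 12.329 − 1.96 × 0.6624) / 0.6538 = 0.843, so power is 80.0%.
- n = 190: (0.15 × 13.784 − 1.96 × 0.6624) / 0.6538 = 1.177, so power is 88.0%.

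**3. Size of the effect under assumed termination rates**

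The documents give no rate, so t, the share of the intensive arm ended in Phase I under item 1, is an assumption throughout. In the worst case every such woman is scored as not having a good birth, so p₂ = 0.40 × (1 − t). All rows use 190 per arm.

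| t | Women (190 × t) | p₂ | Difference (points) | Power |
|---|---|---|---|---|
| 0 | 0 | 0.400 | 15.0 | 88.0% |
| 1% | 1.9 | 0.396 | 14.6 | 86.4% |
| 2% | 3.8 | 0.392 | 14.2 | 84.5% |
| 3.6% | 6.8 | 0.386 | 13.6 | 81.3% |
| 5% | 9.5 | 0.380 | 13.0 | 78.1% |

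Power reaches 80.0% at t = 4.2%, about 8 of 190 women. At t = 3.6%, power is 84.9% if the women keep half their chance of a good birth, and 87.5% if their outcomes are missing at random and left out.

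The 3.6% row is an illustration. In Table 5 the two weight-loss arms of the earlier PCOS trial (50 + 50 women) had no serious adverse events in Phase 1, and the exact upper 95% limit for 0/100 is 1 − 0.025^(1/100) = 3.6%. It is not an orlistat rate. That trial began with sibutramine, one of the two arms also took an oral contraceptive, and suspected allergy is not counted.

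The 88.0% starting point assumes no other dropout. If the planned 20% is also lost, n is 152 per arm, and the same calculation gives 80.0% at t = 0, 78.0% at 1% and 75.8% at 2%.

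**The case against.** The strongest reply is that most of the apparent conflict disappears on a careful reading. Much of that reply stands.

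- **Direct contradiction.** A reader might infer that 9.1.1 and 11.4.1 contradict 5.3. They do not. Section 9.1.1 deals with intolerance, which is a different event. Section 11.4.1 says the drug stops and is silent on whether the woman stays, so a site can obey both. Section 9.1 also continues into women who miss their lifestyle goals, so it could be read as a statement about adherence. The tension with 1.5, 6.1 and the plain words of 9.1 remains.
- **One arm only.** A reader might infer that the standard arm cannot be affected in Phase I. Item 1 covers all medications in the study. Prenatal vitamins go to both arms, and Section 8.1.1 lists their side effects. Known hypersensitivity or contraindication to orlistat is also excluded at entry (Section 5.2, items 16 and 26). The supported statement is that the rule falls mainly on the intensive arm.
- **Missing outcome.** A reader might infer that women who leave have no outcome check at all. Phase I has monthly pregnancy tests, there is a withdrawal visit, pregnancies are tracked to completion, and 5.3 does not say that data collection ends. Section 1.6 defines the endpoint as a good birth during the study, so a woman who leaves not pregnant can arguably be scored as having none. The consent forms and the Manual of Operations were not available and may contain follow-up rules. What stands is that the documents supplied schedule no contact after withdrawal and do not say how a later conception is to be scored.
- **Safety.** Loosening a stop for suspected serious reactions needs care. The fix therefore leaves entry to Phase II to the investigator, so some of these women may still miss clomiphene/IUI.

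**Conclusion.** The point holds as a low-severity inconsistency. Item 1 of Section 5.3, followed literally, ends participation where the neighbouring sections would stop one drug, and in Phase I it bears mainly on the intensive arm. Stopping the drug and keeping the woman in the study serves both her and the intent-to-treat analysis better.

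The effect is probably very small. Section 8.1.3 anticipates no serious adverse events in Phase I, and every rate in the table is assumed. The table should not be read as showing that the trial is underpowered or materially biased: with no other dropout, about 8 of 190 women would have to be removed and all counted as failures before power fell to the stated 80%. The case for the change rests on consistency between sites and on its low cost.

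**What to change.** 1. Reword Section 5.3 item 1 along these lines: *Suspected or confirmed allergic or serious reaction to a study medication: the drug concerned is stopped and the woman remains in the study; entry to Phase II is subject to the investigator's safety judgement.* Keep items 2–4 as safety rules that stop treatment.
2. State in Sections 5.3 and 7.2 that any randomized woman whose study treatment is stopped early is followed by phone or medical records for conception and birth, over the same window as women who stay on treatment, unless she withdraws consent. This would also cover women in either arm discontinued after a second failed cycle (Section 7.2). If the Manual of Operations already says so, a cross-reference is enough.
3. Count her outcome in her assigned arm, as Section 10.9 implies. Record any outside infertility treatment and report births after it separately.

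The cost is a few lines of text and a few calls and record checks. The drawback is that some births after early stopping may reflect outside treatment, because the ban in Section 6.3 applies only during participation; separate reporting makes that visible.
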